Subjects will undergo functional Magnetic Resonance Imaging (fMRI) before and after the study interventions to tests the effects of iTBS vs. placebo on brain’s functional connectivity.

This research will provide meaningful information about the effects of the iTBS intervention on mood and executive function in older adults as well as information regarding the effects of the intervention on brain function. Results of this pilot study will inform a grant submission and allow us to calculate power for a definitive randomized controlled clinical trial to test the efficacy of iTBS and placebo.

A2 Primary Hypothesis

Aim 1. To assess the efficacy of iTBS in improving mood and executive dysfunction in older adults with depression. H_1 . Older adults randomized to iTBS will show significant

decreases in the Montgomery Asberg Depression Rating Scale consistent with improvement, and significant increases in scores on the NIH Toolbox executive domain measures⁵⁻⁷ consistent with executive function improvement compared to those subjects randomized to placebo stimulation (sham).

Aim 2. To test the effects of iTBS on functional connectivity within the Cognitive Control Network (CCN) in depressed older adults using resting state fMRI. H_2 Depressed older adults randomized to iTBS versus sham will have a significant increase in functional connectivity within the CCN.

Aim 3. To examine the association between change in clinical symptoms and neurocognitive assessments and changes on brain connectivity within the CCN. H_3 Among older adults who receive iTBS, changes in connectivity within the CCN will correlate with changes in depression and executive function.

A3 Purpose of the Study Protocol

The purpose of this study protocol is to address the research question of whether intermittent TBS (iTBS) leads to improvement in depression and executive impairment in older adults when compared to placebo. In addition the study will test the effects of iTBS vs. sham (placebo) on functional connectivity within the Cognitive Control Network (CCN) in depressed older adults using resting state fMRI

B Background

B1 Prior Literature and Studies

Late Life depression is associated with executive impairment:

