C1 Primary Aim

Aim 1. To assess the efficacy of iTBS in improving mood and executive dysfunction in older

adults with depression. Hypothesis 1. Older adults randomized to iTBS will show significant decreases in the Montgomery Asberg Depression Rating Scale consistent with improvement, and significant increases in scores on the NIH Toolbox executive domain measures consistent with executive function improvement compared to those subjects randomized to placebo stimulation (sham).

C2 Secondary Aims

Aim 2. To test the effects of iTBS on functional connectivity within the Cognitive Control Network (CCN) in depressed older adults using resting state fMRI. H_2 Depressed older adults randomized to iTBS versus sham will have a significant increase in functional connectivity within the CCN.

Aim 3. To examine the association between change in clinical symptoms and neurocognitive assessments and changes on brain connectivity within the CCN. H_3 Among older adults who receive iTBS, changes in connectivity within the CCN will correlate with changes in depression and executive function.

C3 Rationale for the Selection of Outcome Measures

Depression Measure:

The Montgomery-Asberg Depression Rating Scale, is a standardized mood rating scale, widely used in depression studies. The scale is particularly sensitive to treatment effects, demonstrating greater sensitivity to change (between responders and non-responders) to antidepressant treatment than other scales such as the Hamilton Depression Rating Scale.

Executive function measures:

The flanker inhibitory control, the Dimensional Change Card sort test and the List Sorting Working memory test will measure executive function. These scales are state of the art scales and are recommended by the National Institutes of Health in their NIH Toolbox. NIH Toolbox measures are brief and standardized for assessing function from ages 3 to 85. The NIH toolbox monitors behavioral function over time and across developmental stages. This makes it possible to study changes across the lifespan, and evaluate the effectiveness of a treatment.

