The PI [name] and her designee will meet weekly for research meetings to focus on screening forms; inclusion/exclusion criteria; case report form review; adverse events and other Human Research Protection Office (HRPO) required monitoring and reporting activities. The PI or her designee will record each subject screened for study inclusion and maintain records of reasons for subject exclusions. This information will be included in yearly renewals with the HRPO.

[name] (Professor at the Department of Psychiatry) will be fully available to provide guidance regarding issues related to the safety of study participants and the integrity of the study. [name] will participate in research meetings to review accuracy of screening, subject accrual, and all subjects who withdraw from the study. Likewise, he will be available to assess with issues regarding participant accrual, overall study progress, intervention efficacy, adverse events, ethical concerns, quality of monitoring, and protocol adherence. The entire investigative team with [name] , [name] and the PI Designee will meet at least once per quarter.

We will follow procedures pertaining to adverse events and serious adverse events as specified in the DSMP document

E4 Study Outcome Measurements and Ascertainment

Primary outcome measures:

The effects of the study intervention depression will be measured using the Montgomery Asberg Depression Rating Scale.

The effects of the study intervention on executive function will be evaluated using the Flanker inhibitory control, the Dimensional change sort task and the List Sorting Working memory test will measure executive function, from the NIH Tool box executive function domain.

Brain's connectivity measure: Using resting state fMRI we will measure functional connectivity within the Cognitive Control Network (CCN) in depressed older adults before and after study intervention. We will also explore functional connectivity within and between other networks that are relevant to depression including the Default Mode network and the cingulo-opercular networks.

F Statistical Plan

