Statistical Analyses: We will use intention-to-treat principles. We will use t-test or its non-parametric equivalent to compare the distribution of continuous variables and the changes in the main outcome measures between active and sham groups. χ^2 tests will be used to compare categorical variables between groups. We will use a mixed general linear model (GLM) to accommodate data from our within- and between-participant study design to examine changes from baseline to post-intervention, and compare them between active vs. sham groups. The GLM explores estimated marginal means by taking into account within- and between-participant variability, adjusting for confounders and allowing exploration of significance of within-participant and between-group interaction effects. Differences between groups in behavioral outcome measures and network connection changes will be evaluated through 2-way interaction effect (time*group). Through the 2-way interaction iTBS*Fazekas score we will explore the modification effect of grade of white matter burden on the impact of iTBS in the observed network connectivity changes. Pearson's correlation will examine the correlation between changes in behavioral measures with changes in network connectivity. We will use Hayes' PROCESS¹¹⁴ macro to evaluate the role of the difference in the strength of connections pre-intervention minus the strength of connection post intervention as mediator of change for iTBS and bootstrap and Monte Carlo confidence intervals will be calculated. All statistical tests will be two-sided and evaluated at the alpha level of 0.05. SAS 9.4 (SAS Institute, Cary, NC) and R 3.2.3 statistical software packages will be used for all analyses. Sample size justification: For this pilot study, I plan to enroll 20 elderly subjects and randomized them to iTBS arm or placebo arm (10 in each group). The sample size of 20 subjects is feasible for the time limit of the KL2 award. This pilot sample will provide meaningful data to estimate sample size and calculate power for a subsequent grant application to rigorously test the effects of theta burst stimulation on depressed older adults.

G Data Handling and Record Keeping Records retention:

Study data will be kept for potential future analysis. Records will be maintained for at least 7 years after completion of the study as per local HRPO requirements.

G1 Confidentiality and Security

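### Do the conflicting primary labels for CCN connectivity, and the missing rule for the three Toolbox tests, call for a change to the plan?

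*Combined protocol and SAP*

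**What the plan says.** The combined protocol and SAP describes the outcomes in several places.

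- **A2 Primary Hypothesis** lists all three aims. Under Aim 2 it states that "Depressed older adults randomized to iTBS versus sham will have a significant increase in functional connectivity within the CCN".
- **C1 and C2** are explicit: Aim 1 (mood and executive function) is primary, and Aims 2 and 3 (connectivity, and its association with clinical change) are secondary.
- **E4** has one heading, "Primary outcome measures". MADRS, the Toolbox tests and a separately labelled paragraph on connectivity come after it.
- **H1 in C1** predicts significant "decreases in the Montgomery Asberg Depression Rating Scale consistent with improvement, and significant increases in scores on the NIH Toolbox executive domain measures", relative to sham.
- **C3** names the tests: "The flanker inhibitory control, the Dimensional Change Card sort test and the List Sorting Working memory test will measure executive function". E4 repeats the list. A1 refers to a single battery. Inclusion criterion 4 in D2 averages Flanker and card sort, but for eligibility only.
- **F Statistical Plan** compares changes by t-test (or a non-parametric equivalent) and by a time-by-group interaction, and says "All statistical tests will be two-sided and evaluated at the alpha level of 0.05". It plans 20 subjects, 10 per group, on grounds of feasibility. It gives no rule for combining the Toolbox tests and names no single within-CCN value.

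**The concern.** Two things look wrong. First, one outcome carries two ranks, so a reader cannot tell from A2 or E4 whether a connectivity result would count as a primary finding. Second, H1 is worded as a claim of significance on several executive measures, and the criterion for success is left open. An analyst who has seen the data could call executive function improved because one test crossed 0.05, or not improved because two did not.

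If any one test counts, the chance of a false executive result is more than double that of a single test. If all three must count, power is very low. The results are meant to support a grant application and the power calculation for a larger trial, so an endpoint defined after the fact could carry over into that design. The unnamed CCN summary leaves similar freedom on the imaging side.

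**Working it through.** **Inputs from the plan.** 10 + 10 = 20 subjects; two-sided 0.05 per test (0.025 in the direction favouring iTBS); t-test on change with 18 df; three executive tests. The plan states no power, effect size or familywise error rate, so there is no figure of its own to reproduce beyond the total of 20.

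**Assumptions (not in the documents).** Common correlation r among the Toolbox changes of 0.3, 0.5 and 0.7; MADRS-Toolbox correlation 0.2; where an effect is assumed, 0.8 SD.

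**Bound under independence.** Any of three favouring iTBS: 1 − 0.975³ = 7.3%. In either direction: 1 − 0.95³ = 14.3%.

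**Simulation.** At least 400,000 trials per setting, with t = difference / (pooled SD × √(2/10)) and critical value 2.101. Unless marked two-sided, results count only differences favouring iTBS.

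| Setting and reading | r=0.3 | r=0.5 | r=0.7 |
|---|---|---|---|
| No effect: any of three tests | 6.9% | 6.4% | 5.6% |
| No effect: any of three, two-sided | 13.7% | 12.7% | 11.3% |
| No effect: all three tests | 0.04% | 0.13% | 0.41% |
| No effect: composite | 2.5% | 2.5% | 2.5% |
| No effect: MADRS and at least one test | 0.41% | 0.37% | 0.31% |
| Mood 0.8 SD only: MADRS and at least one test | 3.9% | 3.6% | 3.1% |
| Mood 0.8 SD only: MADRS and composite | 1.6% | 1.6% | 1.5% |

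If the MADRS-Toolbox correlation is 0.4 instead of 0.2, MADRS and at least one test are both falsely positive in about 0.6-0.8%.

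**How often the readings disagree.** With 0.8 SD in all three tests, at least one is significant in 71/65/59% of trials (r = 0.3/0.5/0.7) and all three in 11/16/21%. The two readings of the executive half therefore differ in 59/50/38%. H1 also needs MADRS. If MADRS too improves by 0.8 SD, the readings of H1 as a whole differ in 25/21/16%.

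**What a composite would cost.** An effect in one test only shrinks to (1/3)/√((1+2r)/3) of its standardised size: 0.46 at r=0.3 and 0.37 at r=0.7. Detection of 0.8 SD in one test falls from 41/41/40% (any of three) to 12/10/9%. For an effect shared by all three tests it is 64/55/47%, against 71/65/59%.

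**Precision.** The 95% half-width for any single outcome is 2.101 × √(2/10) = 0.94 SD, under every reading and every label.

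**The labels.** C1 and C2 form the section on study objectives and rank the aims without ambiguity. A2 has a singular title above three aims, which looks like a template heading. In E4 the connectivity paragraph has its own label. C3 uses the same label for a paragraph parallel to those on depression and executive function, so in E4 it may be meant to stand beside the primary heading and not beneath it. Under either label connectivity is tested once by time-by-group interaction at 0.05, and no alpha is shared or passed on between outcomes. The rank does not enter any calculation.

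**The case for a change.** The strongest case for a change is that calling the study a pilot does not settle the matter. Aim 1 speaks of assessing efficacy, H1 and H2 speak of significance, and a primary publication is planned. A verdict on H1 that depends on a reading chosen afterwards is a real freedom: 16-25% of trials under the assumed effects on mood and executive function, and 38-59% for the executive half alone. Stating a rule would cost a few words.

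Most of the factual part stands. The headings do not agree, no rule is stated, and no within-CCN value is named. The documents give no basis for putting a size on that last gap. What does not stand is the inference that the error rate of a stated hypothesis is inflated. The 5.6-6.9% belongs to an any-one reading of half of H1, and the plural wording of H1 could as well be read as requiring all three, which brings the rate to about 0.4% or less. The any/all question also affects only a yes/no label. The three tests and their group differences are the same under every rule, and those estimates are what the later power calculation needs. Section B1 describes three executive domains, and C3 and E4 give a test for each, so separate domain results are a natural default.

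**Conclusion.** No change to the plan follows. The conflict over connectivity is a clerical slip that C1 and C2 resolve, and correcting it would alter no analysis or result. The missing executive rule and the unnamed CCN summary are details that analysts can sensibly fill, by reporting each named test and treating connectivity as secondary. Writing them down would record a choice without showing that the present analysis is wrong. The composite is a trade-off: it holds the executive error at 2.5% in the direction of iTBS but gives up most of the ability to see an effect confined to one domain.

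For MADRS together with at least one Toolbox test, the false-positive rate favouring iTBS is 0.3-0.4% when nothing differs and 3.1-3.9% if only mood improves by 0.8 SD. These figures rest on 10 per arm, assumed Toolbox correlations of 0.3-0.7 and an assumed MADRS-Toolbox correlation of 0.2. The conclusion also depends on the study remaining what section F describes: a feasibility-sized pilot with no familywise claim. It would not carry over to a confirmatory trial with the same wording.

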Executive function deficits are common in late life depression. They are associated with resistance to antidepressants, poor quality of life, considerable disability and increased risk for suicide. No optimal treatments exist for this problem. Selective serotonin reuptake antidepressants do not improve executive impairments and psychotherapy is less helpful with co-occurring executive deficits. Therefore, a safe and well-tolerated treatment is needed to improve executive function, depression burden and overall quality of life. This study will use a novel type of Transcranial Magnetic Stimulation called intermittent Theta Burst Stimulation (iTBS). iTBS uses very high frequency (50Hz) magnetic pulses delivered in “bursts” of 3 stimuli delivered at 50 Hz. It is posited that this intervention induces plasticity in the human cortex. Theoretical and empirical evidence from research studies informs that iTBS is can also improve depression and executive deficits. However such effects have not been examined in older adults.

This project examines iTBS’s ability to improve depression and executive impairment in Late life depression (LLD). In addition the study tests the effects of iTBS on brain connectivity within the Cognitive Control Network (CCN). This study will enhance the understanding of LLD and will provide critical pilot data regarding feasibility to support the development of future randomized controlled clinical trial.

Both active and sham (placebo) interventions will be administered sequentially to the left and right dorso-lateral prefrontal cortex. The total time of stimulation or sham is less than 7 minutes. Active or sham intervention will be administered for 6 weeks (Monday to Friday). A total of 20 subjects will be randomized. Changes in mood from baseline to the end of 6 weeks will be measured using The Montgomery-Asberg Depression scale. Executive function at baseline and end of study will be evaluated with the National Institutes of Health (NIH) Toolbox executive domain battery. Safety assessments will include: The 21 item Scale for suicidal ideation SSI. The frequency, intensity and burden of side effects rating (FIBSER) and the Altman Self Rating Mania scale (ASRM). Ancillary depression measures include the The self-reported Quick Inventory of Depressive Symptoms (QIDS) and the Clinical Global Impression of Improvement scale.

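### Must the plan name which pilot result, the arm difference or the SD of change, will size the later trial?

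*Combined protocol and SAP*

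**What the plan says.** The sample size paragraph of section F gives two reasons for 20 subjects. The first is practical: "The sample size of 20 subjects is feasible for the time limit of the KL2 award". The second is what the data will be used for: "This pilot sample will provide meaningful data to estimate sample size and calculate power for a subsequent grant application". The Study Abstract (A1) agrees on both counts. It says the study "will provide critical pilot data regarding feasibility to support the development of future randomized controlled clinical trial", and later that "Results of this pilot study will inform a grant submission and allow us to calculate power for a definitive randomized controlled clinical trial".

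Neither section names the quantity to be carried forward, whether the arm difference, the SD of change, a correlation or a retention rate. The documents give no target difference, SD, effect value or intended precision.

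The aims are worded more ambitiously than the pilot purpose. A3 sets out to "address the research question of whether intermittent TBS (iTBS) leads to improvement in depression and executive impairment in older adults". Hypothesis 1 in C1 predicts that "Older adults randomized to iTBS will show significant decreases in the Montgomery Asberg Depression Rating Scale consistent with improvement", compared with sham. Hypothesis 2 in C2 predicts that "Depressed older adults randomized to iTBS versus sham will have a significant increase in functional connectivity within the CCN". F compares changes between arms by t-test or its non-parametric equivalent and by a mixed model, two-sided at 0.05.

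**The concern.** Supplying input to a later power calculation is a declared purpose of this trial. With the aims worded as efficacy tests, the arm difference is the result a reader would expect to see carried forward, yet with 10 per arm it is very imprecise. A statistically significant result is especially hazardous as an input, because only a large observed difference can reach significance at this size. A later trial sized from it would tend to be too small. If the input is not named before unblinding, it could also be chosen once the result is known. At stake is the size of the next trial; the conduct and analysis of this one are not affected.

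**Working it through.** **Inputs.** From F: 10 per arm, equal allocation, two-sided alpha 0.05, comparison of changes between arms. Assumed, because the documents are silent: true effect d of 0.5 or 0.8 SD of change, 80% power for the later trial, normal outcomes with equal variances, no dropout. F derives 20 from no formula, so there is no stated figure to reproduce.

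**Precision at 10 per arm** (18 degrees of freedom)
- Half-width of the 95% interval for the arm difference, in SD units: t(0.975, 18) × √(2/10) = 2.101 × 0.447 = 0.94. Under the t-test on changes, an observed difference must be at least this large to be significant.
- 95% interval for the SD of change: 0.76 to 1.48 times the observed SD.
- Power of this trial for one outcome: 18.5% at d = 0.5 and 39.5% at d = 0.8.

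**Sizing from the observed difference.** The required number per arm is 64 at d = 0.5 and 26 at d = 0.8. Required size varies as 1/d², so half or less results when the observed d is at least √2 times the true d. Twice or more results when it is at most the true d divided by √2, and no size can be computed when it is zero or negative. The observed d × √(10/2) follows a noncentral t distribution with 18 degrees of freedom and noncentrality d × √(10/2).

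| True d | Needed per arm | Half or less | Twice or more, or not computable |
|---|---|---|---|
| 0.5 | 64 | 33% | 37% |
| 0.8 | 26 | 25% | 29% |

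The errors fall on both sides, and oversizing is the more frequent. After a significant result the size obtained is at most 19 per arm, with power of 32% at a true d of 0.5 and 67% at 0.8.

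**Sizing from the pilot SD with a fixed target difference.** Write k for target divided by truth. The ratio of the size obtained to the size needed is (s²/σ²)/k². It is one half or less when a chi-square variable on 18 degrees of freedom is at most 18 × 0.5 × k² = 9k².

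| Target | Truth | 9k² | Half or less |
|---|---|---|---|
| equal to truth | 0.5 or 0.8 | 9.00 | 4% |
| 1.0 | 0.8 | 14.06 | 27% |
| 0.65 | 0.5 | 15.21 | 35% |
| 0.8 | 0.5 | 23.04 | 81% |

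Working with whole numbers per arm moves these results by about two points at most (for example 25% instead of 27%, and 34% instead of 35%).

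**Comparison.** The 4% assumes that the true effect is already known, while the 25–33% includes the cost of estimating it. The two are not like for like. A target 25% above the truth (1.0 against 0.8) gives 27%, about the same as the 25% from the observed difference. A target 30% above it (0.65 against 0.5) gives 35%, against 33%.

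**The case for a change.** The strongest case for acting is that F itself makes the later power calculation a reason for the sample size, so it is fair to ask what the pilot will contribute. The omission is real, and the calculations on the observed difference are right under their assumptions. Naming the inputs would cost a few sentences, with no new subjects, visits or data. Writing down a target before unblinding would also remove any temptation to choose the input after seeing the result.

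Part of this stands. A sentence in F would make the purpose clearer, and the wording of Aims 1 and 2 does sit awkwardly beside the pilot purpose in A1 and F. A team that carried forward only a significant observed difference would be making a mistake.

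The rest does not make a case for changing the plan. The documents do not say that the observed difference will be used, so the 25–33% is the risk of an option left open and does not describe a planned calculation. A target difference can instead be set by clinical importance, which is sound practice. But then the needed size is no longer defined by the true effect, and the percentages above stop applying. Fixing targets now would mean committing to values for five measures (MADRS, three executive tests, network connectivity) before the later trial's primary outcome is known. E4 lists connectivity under primary outcomes while C2 makes it a secondary aim, and no document offers a basis for a connectivity target. Early commitment to a poorly founded target recreates the error it is meant to prevent.

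**Conclusion.** No change to the plan is called for. The gap concerns a calculation in a later grant application, where the primary outcome, target difference, power and inputs will have to be justified anyway. Followed as written, the plan yields the data for either approach: the changes in each arm give both the difference and its SD, and confidence intervals for both follow from standard formulas. Nothing in this trial's conduct, analysis or interpretation depends on the choice, and 20 subjects as a feasibility size is not shown to be wrong.

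The size of the issue, for true effects of 0.5–0.8 SD of change, 80% power and no dropout, is as follows. Sizing from the observed difference alone gives half or less of the need in about 25–33% of pilots, and twice or more or no usable answer in about 29–37%. Sizing from the SD gives half or less in about 4% if the target is exactly right, and in about 27–35% if it is 25–30% too large. None of the effect sizes comes from the documents.

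A sensible analyst would report the arm difference and the SD of change with their 95% intervals and justify the later target separately from the observed difference. Saying so in F, and softening the aims to match the pilot purpose, would be optional tidying.
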